### 5 STUDY SCHEDULE

Participants will be recruited for participation by phone call, and phone calls will take place in a private setting.

#### 5.1 SCREENING

The phone screening allows researchers to screen out participants based on self-report responses and for potential participants to become familiar with the study schedule and procedures. During the telephone screening, researchers will provide a brief background about TMS, the timeline of visits, and the time commitment required. The participant will be informed of the compensation amount and payment schedule. The researcher will answer all of the questions posed by the participant. Once all questions have been answered, the participant will be asked if he/she is still interested in participating in the study. If yes, the researcher will ask if the participant will provide verbal consent to begin the initial phone screening which will determine eligibility for the stimulation session. A

*telephone script, which includes the screening questions, is provided in Appendix G.* If the participant is determined to be eligible for participation (no contraindications for TMS or MRI and passes phone screening), then the sessions will be scheduled and a reminder call or email will be given at least 24 hours before each session.

## 5.2 STIMULATION SESSIONS

Participants will undergo five sessions: one screening, one baseline, one MRI, and two active stimulation sessions. At the first session, participants will be guided through the consent form. To ensure that all aspects of the research are understood, participants may be asked a series of questions about the research they are about to take part in (*Appendix E*). Once it is clear that the participant understands the consent form, then they may sign the form.

### Session 1: Screening (2 hours)

- In this initial session, the researcher will explain the procedures for the study, expectations for participation, and participant rights.
- After obtaining written consent, a pregnancy screening will be administered.
- Participant is provided a weblink to completes a series of questionnaires for exploratory purposes. These measures are listed below under “self-report measures.” If these questionnaires are not completed prior to the session, then they are completed here.
- The participant will practice and perform the perception task and the retro-cue working memory task. Participants are given a self-paced break between blocks of the task.
- Participant will receive \$20 in compensation.

### Session 2: Baseline (3 hours)

- EEG net is applied.
- Resting state EEG – Participant will be asked to relax with eyes open and eyes-closed while EEG is collected simultaneously.
- The participant will practice and perform the retro-cue working memory task.
- The participant will practice and perform a simple WM task for color wheel precision.
- Electrodes and net will be removed and participant can wash their hair and face
- Participant will receive \$30 in compensation.

### Session 3: MRI (1 hour)

- Participant undergoes a structural MRI scan.
- Participant performs up to ten-minutes resting state MRI scan in which participant fixates on a point.
- Participant performs working memory task during functional MRI scans
- Participant will receive \$20 in compensation

### Session 4 and 5: Stimulation 1 and 2 (3 hours)

- Motor thresholding using single pulse TMS for use in future sessions will be performed once for each participant on the first day of stimulation, and held constant for the following stimulation session.
- Before practice and performance of the cognitive control task, the TMS coils will be positioned over the targeted region.
- During performance of the task, stimulation will be delivered on every trial.

CONFIDENTIAL

- During stimulation, white noise will be played for the participants to reduce neural effects of auditory entrainment of rhythmic TMS.
- At the end of the session, participants will receive \$40, and \$60 in compensation for sessions 4, and 5, respectively.

## 6 STUDY PROCEDURES/EVALUATIONS

### 6.1 SELF-REPORT MEASURES

Researcher will use a standard questionnaire to screen TMS & MRI candidates. The following questions include the standard contraindications for TMS & MRI research. The TMS contraindications assessment will be administered during the verbal phone screening and for every session prior to stimulation (sessions 4 and 5).

1. Do you have epilepsy or have you ever had a convulsion or a seizure?
2. Have you ever had a fainting spell or syncope? If yes, please describe in which occasion(s)
3. Have you ever had severe (i.e., followed by loss of consciousness) head trauma?
4. Do you have any hearing problems or ringing in your ears?
5. Are you pregnant or is there any chance that you might be?
6. Do you have metal in the brain/skull (except titanium)? (e.g. splint, fragments, clips, etc.)
7. Do you have cochlear implants?
8. Do you have an implanted neurostimulator? (e.g., DBS, epidural/subdural, VNS)
9. Do you have a cardiac pacemaker or intracardiac lines or metal in your body?
10. Do you have a medication infusion device?
11. Are you taking any medications? (Please list)
12. Did you ever have a surgical procedure to your spinal cord?
13. Do you have spinal or ventricular derivations?
14. Did you ever undergo TMS or MRI in the past?

Affirmative answers to one or more of questions 1–13 do not represent absolute contraindications to TMS and fMRI, but the risk/benefit ratio should be carefully balanced by researcher.

In addition to our screening form, we will administer the MRI screening form provided by the Biomedical Research Imaging Center (BRIC) at the University of North Carolina at Chapel Hill. After completion of this form, it is sent to lab technicians at the BRIC who provide additional screening of participants (this form is included in the Appendix). The MRI safety form is completed verbally during phone screening and in person during session 3 (MRI).

In addition, several self-report measures will be collected throughout this study. These measures are listed below and can be found in the attached documents.

- A. THE STATE-TRAIT ANXIETY INVENTORY (STAI) is a 20-item self-report assessment that assesses either temporary or chronic anxiety. For the purposes of this study, the state version will be used to measure anxiety as a result of the stress condition. The STAI is commonly used to assess both types of anxiety, and has applications in both clinical and research settings (Spielberger et al. 1983).
- B. THE BEHAVIORAL INHIBITION AND BEHAVIORAL APPROACH SYSTEM SCALES (BIS/BAS) are a set of 24 questions used to assess an individual's sensitivity to approach vs. inhibition in motivating behavior. This scale is commonly used to measure behavior and has been demonstrated to be reliable (Carver and White 1994).

CONFIDENTIAL

- C. THE POSITIVE AND NEGATIVE AFFECT SCHEDULE (PANAS) is a 20-item self-report assessment using a 5-level Likert scale to assess the positive and negative affect of an individual over the past week. This scale has been shown to be a reliable measure of both positive and negative affect with little subjectivity to demographic variables (Watson et al. 1988).
- D. THE EDINBURGH HANDEDNESS INVENTORY is a 20-item scale to assess the hand dominance of a person in everyday activities (Oldfield 1971).

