### 3.2 EXCLUSION CRITERIA

A potential participant who meets any of the following criteria will be excluded from participation in the study:

- ADHD (currently under treatment)
- Neurological disorders and conditions, including, but not limited to:
  - History of epilepsy
  - Seizures (except childhood febrile seizures)
  - Dementia
  - History of stroke
  - Parkinson's disease
  - Multiple sclerosis
  - Cerebral aneurysm
  - Brain tumors
- Medical or neurological illness or treatment for a medical disorder that could interfere with study participation (e.g., unstable cardiac disease, HIV/AIDS, malignancy, liver or renal impairment)
- Prior brain surgery
- Any brain devices/implants, including cochlear implants and aneurysm clips
- History of current traumatic brain injury
- Failure to pass a colorblindness test
- (For females) Pregnancy or breast feeding
- Anything that, in the opinion of the investigator, would place the participant at increased risk or preclude the participant's full compliance with or completion of the study

**Justifications for any exclusions based on race, gender, or ethnicity:** There are no exclusion criteria based on race, gender, or ethnicity. However, non-English speaking individuals are excluded because the ability to accurately and completely communicate study information, answer questions about the study, and obtain consent are necessary.

**Justification for excluding women or women who become pregnant:** Pregnant participants will be excluded despite the fact that theoretical risk to mother or fetus is exceedingly small, since no safety data for pregnancy is known to exist for TMS studies. Female participants will be asked if there is a possibility that they are pregnant at every stimulation session. If the participant says yes or is unsure, then we will verify pregnancy status via a urine pregnancy test. Only upon a verbal confirmation that pregnancy is not possible or a negative finding will we proceed with the experiment.

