## 9.3 EARLY WITHDRAWAL OF PARTICIPANTS

### 9.3.1 REASONS FOR WITHDRAWAL

A study participant will be discontinued from further participation if:

- The participant meets any exclusion criteria (either newly developed or not previously recognized).
- Anything that, in the opinion of the investigator, would place the participant at increased risk or preclude the participant's full compliance with or completion of the study.

Participants are free to withdraw from participation in the study at any time upon request.

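### Section 6.1 leaves every yes on TMS safety questions 1 to 13 to the researcher's judgement, although 3.2 and 9.3.1 require exclusion or discontinuation for some of those answers

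*Combined protocol and SAP*

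**What the plan says.** Section 6.1 lists the TMS and MRI safety questions and fixes when they are asked: "The TMS contraindications assessment will be administered during the verbal phone screening and for every session prior to stimulation (sessions 4 and 5"). It then gives one rule for a yes on any of questions 1 to 13: such answers "do not represent absolute contraindications to TMS and fMRI, but the risk/benefit ratio should be carefully balanced by researcher". The sentence singles out no question and refers to no other section.

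Section 3.2 is mandatory. Anyone who "meets any of the following criteria will be excluded from participation in the study". The list includes a history of epilepsy, "Seizures (except childhood febrile seizures"), traumatic brain injury, pregnancy or breast feeding, and "Any brain devices/implants, including cochlear implants and aneurysm clips".

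Section 9.3.1 carries the same list forward after entry. Its first ground for discontinuing a participant is: "The participant meets any exclusion criteria (either newly developed or not previously recognized").

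Section 5.1 schedules sessions only for callers who are free of TMS and MRI contraindications and pass the phone screen. Sections 8.3 and 9.2 name screening and exclusion as the means of minimizing seizure risk.

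**The concern.** Some of the 13 questions ask about the very conditions that 3.2 treats as disqualifying. For those answers 3.2 and 9.3.1 leave nothing to weigh, yet 6.1 tells the researcher to weigh. The investigator-opinion item at the end of 3.2 does not supply this latitude: it adds grounds for exclusion and waives none.

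What is at stake is participant safety, not the estimates. Sections 2.2 and 6.2 set stimulation at 120% of motor threshold, with 3000 pulses per session in phase one and 6000 in phase two. Section 8.1 says that the healthy participants gain no immediate benefit, so a risk/benefit balance has no personal benefit to set against a seizure history or a brain implant. In Appendix A the contraindication check is the screening step scheduled at sessions 4 and 5, so the 6.1 sentence is the instruction closest to hand at that moment.

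**Working it through.** No arithmetic applies, and the plan gives no figure to reproduce. The check sets the 6.1 questions against 3.2 and asks whether a yes can occur without meeting an exclusion criterion.

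| 6.1 question | Matching item in 3.2 | Overlap |
|---|---|---|
| 7, cochlear implants | "Any brain devices/implants, including cochlear implants and aneurysm clips" | Complete: every yes meets 3.2 |
| 1, "Do you have epilepsy or have you ever had a convulsion or a seizure" | Epilepsy; "Seizures (except childhood febrile seizures") | Near complete: a yes resting only on childhood febrile seizures is allowed |
| 6, "Do you have metal in the brain/skull (except titanium)? (e.g. splint, fragments, clips, etc") | Aneurysm clips, brain implants | Partial: an aneurysm clip is excluded; splints and fragments are not named |
| 8, implanted neurostimulator | Any brain device | Partial: a deep brain stimulator is excluded; a vagus nerve stimulator is not clearly a brain device |
| 3, severe head trauma | Traumatic brain injury | Partial: the 3.2 wording mixes past and current injury and is unclear |
| 5, pregnant or any chance of it | Pregnancy or breast feeding | Confirmed pregnancy is excluded; a possible pregnancy leads to a urine test under 3.2 and 8.3.2 |

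Most other questions, such as fainting, hearing problems and medications, have no item of their own in 3.2, although its general medical and investigator-opinion items can still catch a particular answer.

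Three answers given at the check before session 5 show where the rules part:

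1. A first seizure since session 4. Section 6.1 tells the researcher to weigh it. Sections 3.2 and 9.3.1 together require discontinuation. The rules conflict.
2. A febrile seizure in childhood. Section 6.1 tells the researcher to weigh it, and 3.2 allows it. There is no conflict.
3. A new medication with no bearing on any 3.2 item. Section 6.1 tells the researcher to weigh it, and 3.2 is silent. There is no conflict.

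A researcher who always decides against proceeding in case 1 satisfies both rules. The fault is that 6.1 also allows the opposite decision, which 9.3.1 forbids. No visible sentence makes 6.1 subject to 3.2 or 9.3.1.

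**The case against.** The strongest reply is that the sections can be applied together. Section 6.1 makes a general statement about the technique and does not say that such a person is eligible for this study; 3.2 decides that, and a specific mandatory rule should prevail over a general remark. Most of the overlapping questions are also wider than the exclusions, so it is correct that a yes does not disqualify automatically. Of the device, seizure and head-injury questions set out above, only question 7 cannot be answered yes without meeting 3.2.

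There are other safeguards too. Section 5.1 bars entry with TMS or MRI contraindications. The visible part of the telephone script asks about brain disease, with epilepsy as its example, and about implanted electronic devices. The MRI form lists cochlear implants, neurostimulators and aneurysm clips, and imaging-center staff screen again. Section 9.2 has the principal investigator review adverse events in real time and decide on continuation.

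All of this stands as to exposure: it makes a wrong decision unlikely. It does not remove the contradiction. Reading 3.2 as superior is sensible, but the reader has to supply that precedence, and 6.1 covers question 7 on the same terms as medications.

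A reader might go further and infer that the protocol permits stimulation of people with epilepsy, or that a seizure first reported at session 4 or 5 is ungoverned because Appendix A schedules the eligibility assessment only at the phone screen and session 1. The documents do not support either reading. The exclusions in 3.2 remain mandatory, and 9.3.1 applies to new and previously unrecognized criteria with no time limit.

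**Conclusion.** The point holds as an inconsistency between safety rules. It is clear for question 7 and for question 1 apart from childhood febrile seizures, and partial for questions 3, 6 and 8. Pregnancy has its own workable rules and needs only a pointer. Researcher judgement is appropriate for answers that meet no 3.2 criterion.

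The size is minor. The documents state no expected number of yes answers, so no rate can be given, and the other safeguards make practical exposure small. No endpoint, analysis or sample size is affected. It still deserves correction because the instruction attached to the last check before stimulation should not be looser than the eligibility rules. The conclusion assumes that no unseen text, such as a separate procedure for staff, already states that 3.2 and 9.3.1 prevail.

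**What to change.** Replace the 6.1 sentence with:

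> An affirmative answer that meets a Section 3.2 exclusion criterion requires exclusion, or discontinuation under 9.3.1, and is not subject to researcher discretion. A yes or unsure on pregnancy is handled under 3.2 and 8.3.2. For other affirmative answers to questions 1 to 13, the researcher carefully balances risk and benefit, subject to the 5.1 requirement that the participant be free of TMS and MRI contraindications.

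The closing reference to 5.1 matters: without it, answers such as a pacemaker or metal fragments would remain discretionary in 6.1 while 5.1 bars anyone with a TMS or MRI contraindication.

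The cost is one replaced passage in 6.1. It adds no visit, test or data item, and the researcher keeps the eligibility review assigned in 12.4.

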## 6.2 SPECIAL ASSAYS OR PROCEDURES

Each participant will receive stimulation in the fourth and fifth sessions, separated by about one week. Motor thresholding will take place in the first stimulation session. For stimulation day, the rhythmic TMS trains are delivered on every trial of the task (there are 600 trials per session). Each train of TMS consists of 5 pulses. There will be a total of 3000 pulses delivered per session in phase one, and with two coils there will be total of 6000 pulses per session in phase two. Each TMS train will be separated by a minimum of 5 seconds. There are three possible trains: individual alpha frequency with an approximate 100 milliseconds inter-pulse interval, individual theta frequency with a 200 milliseconds inter-pulse interval, and arrhythmic with a variable inter-pulse interval (with a minimum of 20 milliseconds inter-pulse interval). The inter-pulse interval, inter-train interval, number of trains, and TMS intensity are all under the safety guidelines set forth by Rossi et al. 2009 and is typical for experiments that deliver online TMS (Hanslmayr et al. 2014; Albouy et al. 2017).

## 6.3 SAFETY MEASURES

We will be monitoring the safety of our participants throughout the study with the following measures. These measures are listed below and can be found in the attached documents.

- A. A stimulation adverse effects questionnaire will be used based on common side effects experience with TMS. This questionnaire will be administered at the end of each session in which the participant receives TMS (sessions 4 and 5). This questionnaire will be used as a safety measure and to collect data on participant experience. Please see *9.1 Safety Parameters* for more information.

## 6.4 LABORATORY EVALUATIONS

### 6.4.1 SCREENING LABORATORY EVALUATIONS

A urine pregnancy test will be performed for all female participants.

INSTRUCTIONS FOR SPECIMEN PREPARATION, HANDLING, AND STORAGE. For this evaluation, an FDA approved commercial home-based kit will be used (HCG Urine Pregnancy Test Strip). Results are available after only a few minutes. Once the results are clear, the researcher will make a note and the sample will be disposed. All samples will be handled using single-use disposable medical gloves.

## 6.5 COGNITIVE TASKS

### 6.5.1 PERCEPTION TASK

The perception task consists of a single epoch. A colored square is presented at fixation with an empty outline of a square adjacent to it. A color-wheel is presented around these two squares. The participant is given two seconds to choose the color from the color-wheel such that it matches the colored square in the center of the screen. Participants move a joystick towards the direction of the color in the color wheel that they wish to select. The square in the center changes color to match the selected color by the

participant. Once the color is selected, the participant pulls the trigger on the joystick with their index finger. Participants are instructed to be both fast and accurate.

#### 6.5.2 RETRO-CUE WORKING MEMORY TASK

The retro-cue working memory task consists of five epochs. In the first epoch, the participant is presented with lateralized stimuli, colored squares, in both the left and right visual hemifield. The participant is given one second to encode these items into memory. During the screening participants will be presented with one, two, or three colored squares in both visual fields, and in subsequent session there is a fixed number of stimuli. In the second epoch, there is a one second delay period over which the iconic memory of the colored squares decays. In the third epoch, the participant is presented with an informative retro-cue, an arrow to the left or right, that is 100% predictive of the upcoming probe, or an uninformative neural cue, an arrow pointing in both directions. In the fourth epoch, participants must maintain the items in memory over a two second delay. It is during this epoch, after the presentation of the retro-cue that TMS is delivered in sessions four and five. Finally, in the probe epoch participants are presented with a dotted outline of the squares on the left or the right and solid lines around the item to be recalled. At the center of the screen is a color wheel and a blank square. Participants move a joystick towards the direction of the color in the color wheel that they wish to select. The square in the center changes color to match the selected color by the participant. Once the color is selected, the participant pulls the trigger on the joystick with their index finger. Participants are instructed to be both fast and accurate.

## 7 STUDY INVESTIGATIONAL PRODUCT

We will use the MagPro X100 system (MagVenture Inc., Alpharetta, Georgia, USA) for transcranial magnetic stimulation. The MagPro X100 is an advanced, high performance magnetic stimulator designed primarily for research purposes. It is a high-quality tool for researchers with a large choice of stimulating parameters and has stimulation rates up to 100 pulses per second at high intensities and the possibility to combine waveforms and pulse modes.

The simulator has several features:

- 3 waveforms: Biphasic, Biphasic Burst and Monophasic.
- Selectable current direction.
- Stimulation rates up to 100 pulses per second.
- Easily connects to external equipment via programmable input/output triggers.
- System operation control via a built-in computer, eliminating the need for an external computer to set up and control the timing of stimulus sequences.
- Controllable from an external device.

### 7.1 SAFETY FEATURES

In the USA, federal law regulates the sale of Medical Devices through the US Food and Drug Administration (FDA). This is done to ensure safety and effectiveness. Devices which are permitted to be marketed for their intended use must either have a 510(k) or PMA clearance.

MagPro® stimulators R20, R30, R30 with MagOption, X100, and X100 with MagOption are all FDA 510(k) cleared (k160280, k061645, k091940 and k150641).

k150641: The intended use is treatment of Major Depressive Disorder in adult patients who have failed to receive satisfactory improvement from prior antidepressant medication in the current episode.

k160280, k061645, k091940: The intended use is for stimulation of peripheral nerves for diagnostic purposes.

The use of devices for other than their FDA cleared intended use is considered as investigational. Such use is only permitted if the Investigational Device Exemption (IDE) guidelines have been followed. For full information on this procedure, please consult FDA's website ([www.fda.gov](http://www.fda.gov)).

All investigational devices must be labeled in accordance with the labeling provisions of the IDE regulation (§ 812.5) and must bear a label with this statement:

"CAUTION Investigational Device. Limited by Federal (or United States) law to investigational use."

